7.1 Discontinuation of Study Intervention

Participants will be withdrawn from treatment for any of the following reasons:

- A participant may withdraw from the study at any time, at his/her own request (i.e, withdrawal of consent), and without giving a reason.
- Occurrence of an exclusion criterion, which is clinically relevant and affects the participant's safety, if discontinuation is considered necessary by the Investigator and/or Sponsor.
- The participant may be withdrawn at any time at the discretion of the Investigator for safety, behavioral, compliance, or administrative reasons.
- Confirmed PD per RECIST 1.1 with the exception that participants receiving treatment may continue past PD if the participant's ECOG PS has remained stable, and if in the opinion of the Investigator, the participant will benefit from continued treatment. See Section 4.1.
- Some ADRs require withdrawal from treatment. See Section 6.8.2 for additional details.
- Drug must not be given to a known pregnant participant.
- Use of a nonpermitted concomitant drug (without approval by the Sponsor and the Medical Responsible), as defined in Section 6.5.2, where the predefined consequence is withdrawal from the study intervention.

Please note: one reinitiating course of treatment at the same dose and schedule and treatment duration up to 24 months is allowed at the discretion of the Investigator and agreement of the Study Medical Responsible for:

- Participants who are experiencing SD, a PR, or CR on either study arm at the time of discontinuation, and then subsequently develop disease progression after stopping therapy, but prior to the end of the study.

OR

- Participants who are discontinued due to an AE that are subsequently well managed or resolved after stopping therapy, but prior to the end of the study.
- Participants meeting the definition of confirmed PD while on-treatment based on RECIST 1.1. (Participants who experience PD may continue treatment with study drugs if the Investigator believes the participant will experience clinical benefit from the treatment and there is no unacceptable toxicity resulting from the treatment. Such participants will be withdrawn from the treatment if any other criteria for withdrawal are met or if alternative treatment options are available and indicated).

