A discussion between the Investigator and Sponsor's Medical Responsible should take place. The Investigator will need to confirm that the benefit of reinitiating treatment outweighs any risk involved, such as that which led to initial treatment discontinuation. For participants with only SD at time of discontinuation, the Investigator should confirm no other reasonable treatment options are available. In addition, to be eligible for reinitiation, the participant must not withdraw consent, and should be followed with regular evaluation scans as specified in Section 1.3 (Schedule of Activities). No cross-over is allowed. Prior to reinitiation of the study intervention, malignant disease must be radiologically restaged within 28 days of dosing to assess all known sites disease. Relevant safety laboratory results must be available and verified prior to reinitiating treatment. Participants who reinitiate treatment will stay on study and will be treated and monitored according to Section 1.3 (Schedule of Activities). A discussion with the study team is warranted to determine if repeating PK/CCl testing is indicated when restarting treatment. A rollover protocol may accommodate M7824 participants if available at the time of reinitiation.

Section 1.3 (Schedule of Activities) specifies the data to collect at study intervention discontinuation and follow-up, and any additional evaluations that need to be completed.

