The on-treatment period is defined as the time from the first IMP intervention to the last IMP intervention date + 30 days OR the earliest date of subsequent anticancer therapy minus 1 day, whichever occurs first, unless otherwise stated. Dates of subsequent anticancer therapy include dates of subsequent anticancer drug therapy, dates of subsequent anticancer radiotherapy, dates of subsequent anticancer surgery. Note that the on-treatment period will include the initial treatment period as well as the reinitiation of treatment period, as applicable. Whether a participant reinitiates treatment (following the rules as outlined in the protocol) or not, the on-treatment period is defined as the time from the first IMP intervention administration to the last IMP intervention administration date + 30 days or the earliest date of subsequent anticancer drug (anticancer therapy, anticancer surgery and anticancer radiotherapy) therapy minus 1 day, whichever occurs first, unless otherwise stated.

For analyses on immune-related adverse events an expanded on-treatment period will be used. See section [15.2.3.2](#) for details.

Definition of duration:

Duration will be calculated by the difference of start and stop date + 1 (e.g. survival time (days) = date of death – date of randomization + 1) (if not otherwise specified).

The time since an event (e.g. time since first diagnosis) will be calculated as reference date minus date of event.

Time since initial cancer diagnosis

Time since initial cancer diagnosis (months) = (date of randomization – date of initial cancer diagnosis)/30.4375

Time since documented, locally advanced, inoperable or metastatic disease

Time since documented, locally advanced, inoperable or metastatic disease (months) = (date of randomization – date of documented, locally advanced, inoperable or metastatic disease)/30.4375

Nicotine consumption: duration of consumption

The duration of nicotine consumption is computed as follows:

- If a subject is a former smoker, the difference in years between end date and start date of nicotine consumption is computed (end date of nicotine consumption – start date of nicotine consumption+1) / 365.25

- If a subject is a current smoker, the difference in years between nicotine consumption collection date and start date of nicotine consumption is computed. (nicotine consumption collection date – start date of nicotine consumption+1) / 365.25

Nicotine consumption: years since quitting

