For data coded according to WHO-DD (e.g., concomitant medications), summaries will be done on the preferred term level where the preferred term is corresponding to codes ending in 01001. With this approach, variations of salt forms of active ingredients will be analyzed under the same term, e.g. diphenhydramine and diphenhydramine hydrochloride will be analyzed as the same preferred term diphenhydramine.

Data collected after reinitiated treatment:

Data collected after reinitiation of treatment will be included in the summary statistics. Data listings will include both data collected during the first period of treatment, and during the reinitiation of treatment (except for listings displaying parameters derived during the first treatment period only). Data collected during the reinitiation of treatment will be flagged.

Re-screened participants

Re-screened participants will be only counted once in the screening analysis set, considering the latest screening (screening with latest informed consent). If a participant is re-screened several times, then he will be counted only once in the disposition table in the number of re-screened participants.

Definition of Pre-, During-, Post-pandemic Time Periods

Participants will be categorized based on the COVID-19 study period defined as:

- Pre-pandemic time period: subjects who started the treatment before the start of COVID-19 pandemic.
- During-pandemic time period: subjects who started the treatment on the same date or after the start of COVID-19 pandemic
- Post-pandemic time period: the end of pandemic is considered not yet reached anywhere at the time of this IAP version redaction, consequently no participant will be grouped into the post COVID-19 study period for this study and no post-pandemic date will be defined.

The start of COVID-19 pandemic is defined by country as the earliest date of either the date of the first death from COVID-19 occurred in each country according to the published data by European Centre for Disease Prevention and Control on 26th June 2020 (<https://www.ecdc.europa.eu/en/publications-data/download-todays-data-geographic->

distribution-covid-19-cases-worldwide) or 11th March 2020 (when the WHO declared COVID-19 pandemic).

Software:

All analyses will be performed using SAS 9.4 or higher in the SAS Grid environment.

10 Study Participants

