15.2.3.2 Immune-related Adverse Events

Immune-related adverse events (irAEs) will be identified programmatically. AEs which satisfy all of the following criteria will be flagged as immune-related:

- 1) The AE preferred term matches a preferred term on the list of pre-selected MedDRA terms.
- 2) The AE onset or worsening occurs after the first study intervention and no more than 90 days after last study intervention, death or to the earliest date of subsequent anticancer therapy minus 1 day, whichever occurs first, unless otherwise stated.
- 3) On the AE eCRF page, the question “Were Corticosteroids, Immunosuppressants, or hormonal therapy (e.g. Thyroid) applied?” has the answer “Yes” selected.
- 4) On the imAE eCRF page, either:
 - a. The question “Does any of the following provide a clear etiology for the event?” has the answer “No” selected, indicating that the AE is not attributable to underlying cancer disease/PD, prior or concomitant medications/procedures, nor another medical condition such as an infection or pre-existing disease.

OR

- b. The imAE eCRF indicates that a biopsy was performed and the question “Is the histopathology/biopsy consistent with an immune-mediated event?” has the answer “Yes” selected.

In the case that criteria (1) through (3) are met, and entries for condition (4) are missing, the following rules will be applied:

- If the answer to “Does any of the following provide a clear etiology for the event?” (4a) is missing, the event will be considered as irAE (irrespective of biopsy results).
- If the answer to “Is the histopathology/biopsy consistent with an immune-mediated event?” (4b) is missing, or if no biopsy was performed, and condition (4a) is not satisfied (i.e. “Yes” is selected as the answer to the question “Does any of the following provide a clear etiology for the event?”), the event will be considered as a non-irAE.

PTs will be compiled into categories on the basis of the list of pre-selected MedDRA terms: Immune-mediated rash, Immune-mediated colitis, Immune-mediated pneumonitis, Immune-mediated hepatitis, Immune-mediated nephritis and renal dysfunction, Immune-mediated endocrinopathies (Adrenal insufficiency, Hypogonadism, Pituitary dysfunction, Type 1 Diabetes

Mellitus, Thyroid disorders), Other immune-mediated myositis, Other immune-mediated adverse events.

Immune-related adverse events (irAEs) will be described in the following tables:

- irAEs
- irAEs by the worst grade

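### Anticancer therapy recorded between stopping and restarting study drug closes the SAP's on-treatment period before the restart, against the SAP's own statement that re-initiation is included

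*SAP*

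**What the plan says.** SAP Section 9 (Definition of on-treatment period) runs the period from the first dose to the last dose plus 30 days "OR the earliest date of subsequent anticancer therapy minus 1 day, whichever occurs first, unless otherwise stated". The triggers are broad: "Dates of subsequent anticancer therapy include dates of subsequent anticancer drug therapy, dates of subsequent anticancer radiotherapy, dates of subsequent anticancer surgery".

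The same paragraph then says: "Note that the on-treatment period will include the initial treatment period as well as the reinitiation of treatment period, as applicable". It goes on to restate the earlier-of-two-dates rule for exactly this group: "Whether a participant reinitiates treatment (following the rules as outlined in the protocol) or not, the on-treatment period is defined as the time from" first dose to the same end point. No exception is made for therapy given before the restart. Later in Section 9, under data collected after reinitiated treatment, the SAP says: "Data collected after reinitiation of treatment will be included in the summary statistics".

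SAP Section 15.2.3.2 makes timing one of the criteria that an irAE must meet. Onset or worsening must be "no more than 90 days after last study intervention, death or to the earliest date of subsequent anticancer therapy minus 1 day", whichever comes first.

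Protocol Section 7.1 provides that "one reinitiating course of treatment at the same dose and schedule and treatment duration up to 24 months is allowed", for participants who progress after stopping with disease control and for those who stopped because of an AE. It requires agreement, restaging and safety laboratory results. One further condition reads: "For participants with only SD at time of discontinuation, the Investigator should confirm no other reasonable treatment options are available". Absence of intervening anticancer therapy is not among the conditions.

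**The concern.** The inclusion sentences and the end rule cannot both hold for a participant who has radiotherapy, surgery or another drug recorded after stopping and who then restarts study drug. The rule is the part that gets programmed, and it ends the period before re-exposure begins.

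Much hangs on this window. It governs TEAEs (SAP 15.1), treatment-emergent laboratory values and worst grades (15.3), vital signs (15.4), the ECOG shift (15.5) and the three-tier analysis (15.2.5). The AESI summaries are based on TEAEs, apart from irAEs, which carry the same cut in their own window. For irAEs the effect goes further than a missed table. An event on restarted drug fails a defining criterion, so it would not be flagged as immune-related and would also be absent from the irAE listing. Participants restarted after an AE are among those for whom toxicity on re-exposure matters most.

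**Working it through.** The plan gives no figure to reproduce, so the check applies the SAP's date rule to illustrative dates. These dates are assumptions, not trial data.

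**Rule.** Let L be the last dose overall, R the first restarted dose, T the first subsequent anticancer therapy, and p = 30 days (90 for irAEs). Assume no death within the window.

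- Window end = min(L + p, T − 1).
- At-risk days on the restarted course = L + p − R + 1.
- Days kept = max(0, window end − R + 1).

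**Assumed dates.** First course days 1–169; restarted course days 281–421. So R = 281 and L = 421. At-risk days are 421 + 30 − 281 + 1 = 171 for TEAEs and laboratory values, and 421 + 90 − 281 + 1 = 231 for irAEs.

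| Case | T | TEAE/lab end | Kept | irAE end | Kept |
|---|---|---|---|---|---|
| (a) no intervening therapy | none | 451 | 171 of 171 | 511 | 231 of 231 |
| (b) radiotherapy before the restart | 240 | min(451, 239) = 239 | 0 of 171 | min(511, 239) = 239 | 0 of 231 |
| (c) new therapy after the last restarted dose | 440 | min(451, 439) = 439 | 159 of 171 | min(511, 439) = 439 | 159 of 231 |

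The result in (b) does not depend on the dates chosen. Whenever T ≤ R, the window ends at or before R − 1, so no day of the restarted course is kept. Case (c) is ordinary truncation.

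**Exposure beside the window.** SAP Section 13 runs treatment duration to the last re-initiated dose. For the bintrafusp alfa arm in case (b) this is (421 − 1 + 14)/7 = 62 weeks, while the safety window covers 239/7 = 34.1 weeks.

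**The case against.** **Intent is stated.** The SAP says twice that re-initiation data are included, and the end rule carries an escape clause for anything stated otherwise. A sponsor could say that the inclusion sentences are that other statement. This stands as evidence of intent. It does not settle the derivation, because the rule is restated after the first inclusion sentence and is addressed to re-initiators by name.

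**The effect is narrower than it may look.** A reader might infer that all re-initiation data are lost. They are not: in case (a) nothing is lost. A reader might also infer that the events vanish from the report. They do not. SAP 15.1.1 lists every AE and flags those in the re-initiation phase, 15.2.2 lists all SAEs, 15.3 keeps and flags laboratory values after the period in listings, and 15.2.1 tabulates all deaths without this cut. A fatal event would be missing from the fatal-TEAE table but not from the death table.

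**Exposure-adjusted rates.** A reader might infer that these are biased. The documents do not show it: SAP 15.2.5 gives those rates their own denominator, so the mismatch is shown only against the descriptive duration table.

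**The sequence may be rare.** Protocol 6.5.2 bars concurrent anticancer treatment, and 7.1 makes non-permitted drugs a reason to stop. But those rules concern use alongside study drug, not the interval after stopping. Protocol 4.1.2 foresees study drug resuming after local treatment of brain metastases or surgical removal of a lesion. Whether such treatment would be recorded on the post-discontinuation pages (SAP 12.5) or as a concomitant procedure (SAP 12.3) cannot be seen from the documents.

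**The study was stopped.** True, but the single reporting analysis in SAP 6.6 still includes the safety tables.

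**Conclusion.** The point holds for one group: re-initiators with a recorded anticancer drug, radiotherapy or surgery between stopping and restarting. For them the rule, followed as written, removes the whole restarted course from the treatment-emergent, worst-grade laboratory, AESI and irAE tables and prevents irAE classification. Other re-initiators are not affected by this gap in the rule.

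This is an unreconciled contradiction within the SAP, and the text does not support reading it as a deliberate decision to exclude re-exposure data. The documents do not say how many participants had this sequence; the number is probably small and could be very small. The conclusion assumes that the derivation follows the rule literally and that the intervening treatment is recorded as subsequent therapy. The change is worth making because the loss is complete for each affected participant and the correction is cheap.

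**What to change.** In SAP Sections 9 and 15.2.3.2, let only anticancer therapy that starts after the last dose overall close the window: end = min(last dose + 30 days [90 for irAEs], first such therapy − 1 day). The limit at death in the irAE criterion stays. Flag events that occur after intervening therapy. In case (b) the TEAE window then ends on day 451 and keeps 171 of 171 days; case (c) stays at day 439.

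The cost is one condition in the derivation and two SAP sentences. The downside is that some events in the off-drug gap after other therapy become TEAEs: in case (b), those on days 240–280, which is 41 days. The present rule already counts the whole gap for re-initiators without intervening therapy, so this is not new in kind.

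If the gap should not count, define one window per course instead. In case (b) these are days 1 to min(169 + 30, 239) = 199 and days 281–451, leaving out days 200–280 (81 days).

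Whichever is chosen, align both Section 9 statements and the irAE criterion. Also check the AE reporting period. Protocol 8.2 ends it before the start of any anticancer therapy, while 8.3.1 has no such stop. Those passages must be reconciled, since an analysis window cannot recover events that were not collected.

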10.1 Disposition of Participants and Discontinuations

Descriptive statistics will be used to summarize participant disposition and reason for discontinuation, based on the electronic case report form (eCRF) data.

The following information will be reported:

- Total number of participants prescreened
- Number of participants who did not continue beyond prescreening overall and grouped by reason (reason related to central testing, reason related to local testing, reason independent of local/central testing)
- Number of participants who completed the pre-screening (pre-screening ICF signed), but have not signed the main ICF yet
- Total number of screened participants
- Total number of re-screened participants
- Number of participants who did not continue beyond screening overall and grouped by reason (participant did not meet all eligibility criteria, withdrew informed consent, progressive disease, adverse event, lost to follow-up, death, other)
- Number of participants who completed the screening (main ICF signed), but have not been randomized yet
- Number of randomized participants overall and by treatment arm
- Number of randomized participants who did not receive any treatment
- Number of randomized participants with treatment on-going in each treatment arm
- Number of randomized participants off treatment, grouped by treatment arm and main reason
- Number of randomized participants with treatment reinitiated
- Number of randomized participants with treatment on-going after reinitiation
- Number of randomized participants who discontinued treatment after reinitiation

- Number of randomized participants who discontinued the treatment but are still in study for follow-up, grouped by treatment arm
- Number of randomized participants who discontinued the study, grouped by treatment arm and main reason (as reported on “Study termination” page of the eCRF).

In addition, the number of participants in each analysis set defined in Section 8.2 will be summarized. The percentage of participants with percentage based on the number of participants in the FAS population will be presented. The disposition of participants may also be presented with some PD-L1 assay information in a CONSORT diagram (e.g. PD-L1 assay test performed for the inclusion; Dako 73-10, CCI [REDACTED] results). The discrepancies between planned and treated arms will be cross-tabulated and provided in a listing. The number of randomized participants as per Interactive Response Technology (IRT) by region and country will be provided, as well as the number of participants by randomization strata (as per IRT).

For the IDMC meetings, timeliness and Cleanliness of the data will be summarized as follows:

For participants who are still on treatment:

- Number of participants with last on-study safety information (AEs, Labs, VS, Other safety evaluations: ECG, ECOG) entered into the data extract
 - Within 1 month prior to the data cutoff date
 - Between 1 and 2 months prior to the data cutoff date
 - Between 2 and 3 months prior to the data cutoff date
 - More than 3 months prior to the data cutoff date
 - No information

For participants who have had their end of treatment visit:

- Number of participants in the follow-up phase with and without follow-up information
- Among participants with follow-up information, number of participants without a death report in the follow-up phase
- Among participants with follow-up information and no death report in the follow-up phase, number of participants with last follow-up date (from the Participant Status/Survival Follow-Up eCRF page)
 - Within 1 month prior to the data cutoff date
 - Between 1 and 2 months prior to the data cutoff date
 - Between 2 and 3 months prior to the data cutoff date
 - More than 3 months prior to the data cutoff date

The listing of participant disposition will include all participants (i.e. pre-screened participants, pre-screening failures, participants included in screening, screening failures, but not re-screened participants). The listing will include the following information (if applicable): planned arm (participants having actual arm different from planned arm will be flagged and displayed in a separate listing), participant identifier, date of prescreening informed consent, included in the screening phase and reason for exclusion, date of main informed consent, included in the study, reason for exclusion, randomization date, first/last treatment date, reason off-treatment, date and reason off-study, population flags. When the reasons, such as the reason off-treatment is categorized as “Other, specify” or “Withdrew consent from treatment, specify”, the verbatim text as entered in the eCRF will be presented in the listing.

If any re-screened participants will be observed, the listing of re-screened participants will be provided and will include the following information: planned arm, participant identifier, date of informed consent, randomization date, participant identifier at screen failure, date of informed consent at screen failure, date of screening failure, reason of screening failure.

In addition, a listing of participants for which study treatment has been reinitiated will be provided with the following information: participant identifier, date of randomization, planned treatment, date of first IMP intervention, date of last IMP intervention, date and reason for treatment termination (if treatment is discontinued), as applicable.

For the IDMC meetings, Kaplan-Meier’s plots of time to treatment discontinuation and time to study discontinuation will be provided (if more than 10 events will be observed).

In addition, for the assessment of COVID-19 impact on this study, an overview table will be presented by treatment arm with the following information:

- Subjects potentially affected by COVID-19 (i.e. subjects who started treatment after start of the COVID-19 pandemic, or who started treatment prior to start of the COVID-19 pandemic and are still ongoing after the start of the pandemic)
- Subjects with at least one COVID-19 impact
- Subjects with at least one COVID-19 impact in the following categories: adverse events, death, protocol deviations, missed drug administration, treatment administration modifications, missed tumor assessments, delayed tumor assessments, missed visits, tele-visits replacing on-site visits, treatment discontinuation, study discontinuation.
- Number of subjects with missed tumor assessments, delayed tumor assessments, missed visits, tele-visits replacing on-site visits (1 / 2 / 3 / >3)

The frequency distribution of participants who started the treatment before or during the pandemic per country-specific start of COVID-19 study period (see Section 9 for details on the COVID-19 categorization by study period) will be also displayed.

A listing of COVID-19 impact will be provided with the following information: treatment arm, participant identifier, first and last date of treatment administration, date of the event, visit, category, event, event description/reason

